### **Plan for alerting the staff for side effects**

The most common side effects are gastrointestinal. To reduce the incidence of these side effects, the dose of metformin will be slowly increased and will be given with meals. In the event of intolerable gastrointestinal side effects, the participant will contact the study coordinator via phone call (provided at the time of consent and enrollment). The study coordinator will inform the Principal Investigator and will determine whether a dose reduction is needed (which will be done over the phone) or the participant needs an additional visit. The study coordinator will make a follow-up phone call in one week to inquire whether the side effects have improved/resolved. If they have, the participant will continue with the protocol. If the participant needs to come in due to severity of side effects or the side effects don't resolve, the PI will see the participant and in consultation with the endocrinologist will determine whether to continue the drug, lower the dose, or stop the drug. If the drug is stopped, the final measurements will be done at that time.

**Blinding:** To ensure blinding, we will take the following steps. The investigators will be blinded to the treatment assignment. The pill count, change in the metformin dose, adverse effect reporting, data entry in the case report form (CRF) will be done by the main study coordinator. Measurement of frailty, MMSE, Katz ADL is done by a second study coordinator who will be unaware of the drug assignment. The pharmacist will not be involved in the routine care or follow-up of these patients. If the discontinuation of study drug is due to serious adverse effects, the principal investigator will contact the primary care provider and further management will be instituted.

**Molecular markers:** 50 mL of whole blood will be collected for omics assessment. EDTA tubes will be used by the CRTU staff to collect serological samples. The samples will be sent via pneumatic tube shuttle to the Hilton building for pick up by the [name] study team. Samples will be spun down, processed and/or stored for omics analysis. Study samples will be logged into the RLIMS system for sample management. Five randomly selected serological samples will undergo ELISA-based array evaluation to simultaneously quantify 1200 unique cytokines and growth factors. For non-stochastic evaluation, column-based immunodepletion will be utilized to eliminate albumin from five randomly selected samples prior to 2D-Gel separation and MS spectrometry-based deconvolution to establish the serum proteome. Serum samples will also undergo density filtration followed by rapid lyophilization or density concentration for isolation of the exosomal fraction. Purified serum exosomes will be enriched for small RNAs and subjected to miRNomics analysis. Data sets collected from this cohort will be cross-referenced with clinical frailty following chronic metformin treatment to document regenerative impact at the molecular level. This clinomics-based profiling will provide biomarker

readout to yield a systems-biology map of the mechanistic basis for regenerative benefit in those responsive to metformin therapy. The remaining samples will be stored for future use.

**Serum SASP markers:** will be measured at baseline, 3 months, and 12 months on all subjects. Serological markers of senescence will include [interlukin-6 (IL-6), matrix metalloproteinase (MMP) 3, 9, and 12, PAI-1 and -2, activin A, and monocyte chemotactic protein (MCP)].

**Optional Microbiome Sub- Study protocol:** The optional stool samples will be labeled with an ARLIMS tracking number and will be frozen at -80C. At study completion, samples will undergo DNA isolation and subjected to Ribosomal DNA evaluation to delineate and speciate the microbiological content of the stool (Microbiome). For those who agree, a patient stool sample kit will be mailed to each patient prior to their outpatient appointment and will be collected in a fecal tube collection kit prior to their outpatient visit at baseline, 3 month and 12 months. The patient will bring the kit at time of appointment and the sample will be stored in a secured research facility for microbiome analysis. The Mayo Clinic Clinical Research Trials Unit will assist in stool sample pick-up and short-term -80°C storage prior to study staff retrieval.

**Food Frequency Questionnaire:** An electronic VioFFQ food frequency questionnaire will be administered to those who consent to optional microbiome sub-study, from Viocare Technologies, Inc. to determine dietary patterns over the last 90 days; completed, de-identified questionnaires will be analyzed by a Mayo Clinic research dietician and returned to study staff.

**Self-Report:** A brief self-report regarding recent use of antibiotics, laxatives, and colonoscopy colon prep agents will be distributed to consenting patients and considered as metadata. These responses may be verified by study staff in a chart review where possible.

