**I. Human study issues:**

**Human Subjects Safety:** An independent, internal data and safety monitoring board (DSMB) will oversee the progress and safety of the trial and will advise the investigators whether to continue, modify, or terminate the trial. Potential risks to participants may include side effects from metformin.

Protection of patient's identity will follow the Department guidelines for handling and storage of research data. Standardized systems to ensure patient confidentiality will be maintained.

Medication safety will be ensured by not giving metformin to anyone who has history of hypersensitivity to metformin or who have moderate-to-severe renal impairment (GFR<45mL/min/1.73m^2). Participants on metformin will discontinue the drug to prevent lactic acidosis if they will have a radiologic study with contrast, surgery, excessive alcohol intake, or any other precipitating factors. The only other serious adverse effect of hepatitis will be periodically monitored by blood tests, including serum bilirubin, ALT and AST.

**Early withdrawal of Subjects:** Participants with serious adverse effects from the medications will discontinue medication use, but will continue with the study visits, unless they wish to completely withdraw from the study. We will make arrangements for the participant to be seen by their primary MD for follow-up. At any other time, patients will contact the main study coordinator, if they develop and want to report any side effects. We will also discontinue medication use if the participants fail to follow the protocol or are unwilling to continue the prescribed medication.

Patients who discontinue the drug will come for their final check-up and will include frailty assessment, and blood draw for biomarkers. We would use intention-to-treat analyses and would not add any other subjects. The subjects who discontinue the study drug will be followed-up by a phone call at one month. If the discontinuation is due to serious adverse effect, the patient will be asked to contact the primary care provider and further management will be instituted.

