The onset of lactic acidosis often is subtle, and accompanied only by nonspecific symptoms such as malaise, myalgias, respiratory distress, increasing somnolence, and nonspecific abdominal distress. There may be associated hypothermia, hypotension, and resistant bradyarrhythmias with more marked acidosis. The patient and the patient's physician must be aware of the possible importance of such symptoms and the patient should be instructed to notify the physician immediately if they occur. Metformin should be withdrawn until the situation is clarified. Serum electrolytes, ketones, blood glucose, and if indicated, blood pH, lactate levels, and even blood metformin levels may be useful. Once a patient is stabilized on any dose level of Metformin, gastrointestinal symptoms, which are common during initiation of therapy, are unlikely to be drug related. Later occurrence of gastrointestinal symptoms could be due to lactic acidosis or other serious disease.

Levels of fasting venous plasma lactate above the upper limit of normal but less than 5 mmol/L in patients taking Metformin do not necessarily indicate impending lactic acidosis and may be explainable by other mechanisms, such as poorly controlled diabetes or obesity, vigorous physical activity, or technical problems in sample handling.

Lactic acidosis should be suspected in any diabetic patient with metabolic acidosis lacking evidence of ketoacidosis (ketonuria and ketonemia).

Lactic acidosis is a medical emergency that must be treated in a hospital setting. In a patient with lactic acidosis who is taking Metformin, the drug should be discontinued immediately and general supportive measures promptly instituted. Because metformin hydrochloride is dialyzable (with a clearance of up to 170 mL/min under good hemodynamic conditions), prompt hemodialysis is recommended to correct the acidosis and remove the accumulated metformin. Such management often results in prompt reversal of symptoms and recovery.

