*Change in clinical status of patients with previously controlled type 2 diabetes*—A patient with type 2 diabetes previously well controlled on Metformin who develops laboratory abnormalities or clinical illness (especially vague and poorly defined illness) should be evaluated promptly for evidence of ketoacidosis or lactic acidosis. Evaluation should include serum electrolytes and ketones, blood glucose and, if indicated, blood pH, lactate, pyruvate, and metformin levels. If acidosis of either form occurs, Metformin must be stopped immediately and other appropriate corrective measures initiated.

*Hypoglycemia*—Hypoglycemia does not occur in patients receiving Metformin alone under usual circumstances of use, but could occur when caloric intake is deficient, when strenuous exercise is not compensated by caloric supplementation, or during concomitant use with other glucose-lowering agents (such as sulfonylureas and insulin) or ethanol.

Elderly, debilitated, or malnourished patients, and those with adrenal or pituitary insufficiency or alcohol intoxication are particularly susceptible to hypoglycemic effects. Hypoglycemia may be difficult to recognize in the elderly, and in people who are taking beta-adrenergic blocking drugs.

*Loss of control of blood glucose*—When a patient stabilized on any diabetic regimen is exposed to stress such as fever, trauma, infection, or surgery, a temporary loss of glycemic control may occur. At such times, it may be necessary to withhold Metformin and temporarily administer insulin. Metformin may be reinstated after the acute episode is resolved.

The effectiveness of oral antidiabetic drugs in lowering blood glucose to a targeted level decreases in many patients over a period of time. This phenomenon, which may be due to progression of the underlying disease or to diminished responsiveness to the drug, is known as secondary failure, to distinguish it from primary failure in which the drug is ineffective during initial therapy. Should secondary failure occur with either Metformin or sulfonylurea monotherapy, combined therapy with Metformin and sulfonylurea may result in a response. Should secondary failure occur with combined GLUCOPHAGE/sulfonylurea therapy or metformin XR/sulfonylurea therapy, it may be necessary to consider therapeutic alternatives including initiation of insulin therapy.

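### The side-effect alert plan does not separate early from late gastrointestinal symptoms and does not refer to the Appendix 1 warning that late ones may be lactic acidosis

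*Protocol*

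**What the plan says.** **Alert plan (section G, Plan for alerting the staff for side effects).** The entry point is "In the event of intolerable gastrointestinal side effects, the participant will contact the study coordinator via phone call". The principal investigator is told of the call, and the next step is that the coordinator "will determine whether a dose reduction is needed (which will be done over the phone) or the participant needs an additional visit". A second contact is then planned: "The study coordinator will make a follow-up phone call in one week to inquire whether the side effects have improved/resolved". Where severity requires a visit, or symptoms persist, "the PI will see the participant and in consultation with the endocrinologist will determine whether to continue the drug, lower the dose, or stop the" study medication. No step depends on how long the participant has been on treatment, and Appendix 1 is not cited.

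**Appendix 1 (Warnings, Lactic Acidosis).** The onset is described as subtle, with a list of vague symptoms that includes abdominal distress. For these, "the patient should be instructed to notify the physician immediately if they occur", and metformin is to be taken away while the cause is established. Blood tests, among them electrolytes, pH and lactate, are named as possibly useful. The same paragraph then separates gastrointestinal symptoms by time: common at the start of therapy, but probably not drug effects once a dose level is stable. It concludes: "Later occurrence of gastrointestinal symptoms could be due to lactic acidosis or other serious disease".

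**Other provisions.** Administration of Metformin (section G) stops the drug for hospitalisation or acute conditions that can harm renal function or lead to lactic acidosis, and for significant adverse effects. Human Subjects Safety (section I) stops it for contrast studies, surgery, excessive alcohol and other precipitants. Study visits (section G) cites Appendix 1 only where it withdraws subjects with serious side effects.

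**The concern.** The alert plan is what the coordinator will follow when a participant phones. It treats a gastrointestinal complaint as a question of tolerability and does not ask when the complaint began. The appendix says the same complaint means something different once the dose is stable.

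A participant who calls months into treatment could have the dose lowered by phone and be contacted again a week later, still on drug. The appendix points towards withdrawal and clarification. At stake is delay in recognising a rare event that the appendix describes as fatal in about half of cases, in frail people aged 60 or over with coronary disease. The appendix adds that the risk rises with age and with renal dysfunction.

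**Working it through.** The protocol gives no figure to reproduce here, so the check is mainly a comparison of texts, with a short calculation of scale.

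**1. The two texts side by side**

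| Question | Alert plan, section G | Appendix 1, Lactic Acidosis |
|---|---|---|
| Does timing matter? | Not mentioned | Yes: initiation versus after stabilisation |
| Presumed cause of a late complaint | Side effect of study drug | Probably not the drug at a stable dose; possibly lactic acidosis or other serious disease |
| Drug in the meantime | Reduced dose by phone, or a visit; stopping is an option at the later step | Withdrawn while suspicious symptoms are clarified |
| Reassessment | Phone call in one week, unless a visit is arranged | Immediate notification of the physician; blood tests may be useful |

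One caution on the right-hand column: the sentences on withdrawal and immediate notification are attached to the list of vague symptoms. The sentence on late gastrointestinal symptoms follows in the same paragraph. Abdominal distress is on that list, so the two overlap.

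**2. Do other provisions close the gap?**

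- Administration of Metformin addresses conditions that can cause lactic acidosis, not symptoms that may signal it. Significant adverse effects are not defined.
- Human Subjects Safety lists precipitants, not symptoms.
- Study visits and the Stopping Rules act on serious side effects, so the event must already have been recognised as serious.
- The Schedule of Events lists no lactate, electrolytes or bicarbonate, and no visit between month 3 and month 12.

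None of these tells the coordinator that a late gastrointestinal complaint differs from an early one.

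**3. How much of the year is late?** Dosing starts at 500 mg twice daily (1,000 mg/day) and rises weekly to at most 2,000 mg/day. The step is not stated. Assuming 500 mg/day per step, (2,000 − 1,000)/500 = 2 steps, or about 2 of 52 weeks. If dose adjustment instead lasted until the 3-month visit, 12 − 3 = 9 months would remain. Either way, most of the treatment year falls after titration.

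**4. Expected cases of lactic acidosis.** Inputs: 12 participants randomised 1:1, so 6 on metformin (assuming an even split), one year each; 0.03 cases per 1,000 patient-years and about 50% fatality (Appendix 1).

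- Expected cases: 6 × 1 × 0.03/1000 = 0.00018.
- Expected fatal cases: 0.00018 × 0.5 = 0.00009.
- If the risk in this population were 10 to 100 times higher (an assumption): 0.0018 to 0.018 cases.

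**5. A figure that does not measure the problem.** Appendix 1 reports diarrhoea in 53.2% on metformin. For 6 participants this gives 6 × 0.532 = 3.2 expected, and a probability of at least one of 1 − 0.468^6 = 0.99. But it counts any diarrhoea, in patients with type 2 diabetes on up to 2,550 mg/day. It is specific neither to intolerable symptoms nor to late ones. It says nothing about how often the two texts would conflict.

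**The case against.** The strongest reply is that the alert plan is not phone dose reduction alone. The principal investigator hears of the call, the same sentence offers a visit, and severe or persistent symptoms reach the investigator and the endocrinologist, who may stop the drug. The paragraph opens with slow dose increase, so its authors may have had titration in mind; that it applies all year is inferred from the absence of a limit. Vomiting that causes dehydration might trigger the stopping provision under Administration of Metformin. The appendix is part of the protocol, and its language on late symptoms is conditional.

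All of this stands. It shows that a late complaint could be handled as tolerability, not that it would be. It does not remove the gap, because nothing in the plan prompts the question of onset and the call-back branch remains open to a late caller.

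A reader might infer more, and the protocol does not support it:

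- **That only intolerable gastrointestinal effects can be reported.** Early withdrawal of Subjects (section I) lets participants report any side effect to the coordinator, and side effects are asked about at each visit.
- **That section I overlooks lactic acidosis when it says** "The only other serious adverse effect of hepatitis will be periodically monitored by blood tests". That sentence directly follows the one on lactic acidosis, so other means other than lactic acidosis.
- **That hypoglycaemia is a parallel omission**, given "Hypoglycemia may be difficult to recognize in the elderly, and in people who are taking beta-adrenergic blocking drugs". The same appendix paragraph says it does not usually occur on metformin alone, and section G calls it rare.
- **That participants are not told which symptoms to report.** Consent pages are not available for review, so this cannot be judged.
- **That the trial's safety result would be biased by misfiled events.** The alert plan sets no coding rule, so this is speculation.

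**Conclusion.** The point holds as an inconsistency in safety procedure, not as a numerical error or a demonstrated hazard in this trial. The alert plan draws no line between symptoms during titration and symptoms after a stable dose. It does not refer to the Appendix 1 warning that draws that line, and no other provision supplies it.

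The chance that a case passes through the gap is very small: 0.00018 expected cases, or 0.018 even at an assumed hundredfold risk. The reason to act is the severity of the event and the ease of correction, so this is a worthwhile correction of moderate weight. The conclusion assumes an even split of 6 per arm, a full year on treatment, the appendix incidence, and that no separate call procedure, unseen here, already carries the warning.

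**What to change.** Reconcile four places in the protocol: the alert plan and Administration of Metformin in section G, Human Subjects Safety in section I, and the lactic acidosis warning in Appendix 1. After the change, the alert plan and the coordinator's call procedure should be consistent with the warning on late gastrointestinal symptoms and should refer to it. Which clinical rule applies is for the sponsor and the endocrinologist to decide; none is proposed here.

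The cost is a change of wording in the protocol and the call procedure, and possibly an occasional extra unscheduled check for a complaint that proves benign. Sample size, visits and endpoints are unaffected.

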## **(MATE) Metformin and Aging Trial in the Elderly: A Pilot and Feasibility Study**

**Abstract.** Metformin exerts its effect on health span as a calorie restriction-mimetic through activation of AMP-activated protein kinase. This drug is safe, inhibits cellular senescence, and prolongs life in mammals. We hypothesize that chronic metformin administration through augmentation of cellular regeneration and inhibition of senescence improves physical functioning of older adults. In this pilot, feasibility study, we aim to administer metformin up to 2 gm or placebo in a 1:1 randomized fashion for one year to 12 frail adults,  $\geq 60$  years with coronary artery disease and assess their physical function by frailty measures. Among patients with improved physical function throughput profiling of tissue and serological samples will be made to establish a molecular map of the impact of metformin. The effect of metformin on several senescent markers (IL-6, MCP-1, MMP-3/9/12, PAI-1/2, and activin A) will be tested as well.

Version: 4

Date: October 5, 2020

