**E. Brief Synopsis of Methods:** 12 frail patients  $\geq 60$  years with CAD, will be randomized to metformin (up to 2.0 gm) or placebo for 1-year to note improvement in frailty. Molecular map through high throughput serological profiling and assessment of SASP will be done of responders and nonresponders to metformin. An IND exemption is being requested for the use of metformin.

**F. Preliminary data to support feasibility:** In a prospective cohort study, patients  $\geq 65$  years who underwent PCI were assessed for frailty (Fried criteria), comorbidity (Charlson index), and quality of life [SF-36]. Of the 628 patients discharged, 78 died. Following adjustment, frailty was associated with long-term mortality. In a recent pilot study, oral rapamycin (0.5, 1, 2.0 mg) was given for 12 weeks to 13 non-frail patients who underwent PCI. Plasma and adipose tissue markers of senescence were favorably modified by rapamycin [plasma IL-6 decreased from 4.4 to 2.6 pg/ml; adipose tissue mRNA expression of p16 (129 vs. 169), and senescence-associated beta galactosidase activity decreased (2.2% vs. 3.6%). Moderate correlation between some senescence markers and physical functioning was also demonstrated.

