#### Schedule of Events

Tests	Screening Visit	Baseline Visit	3 Month Visit (at conclusion of CR, ± 2 weeks)	12 Month Visit (± 2 weeks)
Informed Consent	X			
Randomization		X		
CBC (without differential)		X	X	X
Serum Albumin		X	X	X
Blood Urea Nitrogen (BUN)		X	X	X
Creatinine (serum)		X	X	X
AST		X	X	X
ALT		X	X	X
Bilirubin (total)		X	X	X
Bilirubin (direct)		X	X	X
Fasting lipid panel		X	X	X
Blood sample collection for molecular & SASP markers		X	X	X
Frailty assessment	X	X	X	X
Mini-Mental State Examination (MMSE)	X		X	X

Katz Index of Independence in ADL		X	X	X
Stool sample (optional sub-study)		X	X	X
Food Frequency Questionnaire (optional sub-study)		X	X	X
Self-report of antibiotics, laxatives, and colonoscopy history		X	X	X

**H. Statistical analyses and power considerations:** This is a pilot study and will not be powered to detect specific effect sizes. Importantly, measures of variation from this study will be used to power future studies.

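### Five random samples for the 1200-analyte array and for the serum proteome do not match the responder-based profiling that the protocol describes elsewhere

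*Protocol*

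**What the plan says.** Section G, Molecular markers, sets the selection rule for two platforms. For the array: "Five randomly selected serological samples will undergo ELISA-based array evaluation to simultaneously quantify 1200 unique cytokines and growth factors". For the proteome: "column-based immunodepletion will be utilized to eliminate albumin from five randomly selected samples". Neither sentence names an arm, a visit or a response group, and the text does not say whether both platforms use the same five samples.

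The same paragraph states what the data are for: "Data sets collected from this cohort will be cross-referenced with clinical frailty following chronic metformin treatment", giving a biomarker "readout to yield a systems-biology map of the mechanistic basis for regenerative benefit in those responsive to metformin therapy".

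Two other places describe the profiled population differently. The Abstract: "Among patients with improved physical function throughput profiling of tissue and serological samples will be made". Section E: "Molecular map through high throughput serological profiling and assessment of SASP will be done of responders and nonresponders to metformin".

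The Abstract gives the size and allocation, "or placebo in a 1:1 randomized fashion for one year to 12 frail adults". The Schedule of Events lists "Blood sample collection for molecular & SASP markers" at baseline, 3 months and 12 months.

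**The concern.** A random draw and a choice by response are different rules. An unrestricted draw can consist largely of placebo and baseline samples, which say nothing about the state of a metformin responder under treatment. The three descriptions also differ among themselves: a frame of improved patients holds no nonresponders, while section E wants both groups.

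With only five assays per platform, the frame largely decides whether these two data sets can address their stated purpose. If the frame stays open, it can also be chosen after results are known.

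**Working it through.** The protocol gives no figure to reproduce here, so the check counts what a draw of five would contain.

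**Inputs from the protocol**
- 12 participants at 1:1 (Abstract), so 6 on metformin if exactly balanced.
- 3 blood draws each (Schedule of Events): 12 × 3 = 36 scheduled samples.
- Metformin samples after baseline: 6 × 2 = 12. Placebo or baseline samples: 36 − 12 = 24.
- 5 samples per platform (section G, Molecular markers).

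**Assumptions, not in the protocol**
- r of the 6 metformin participants respond, r = 1 to 5, and n = 6 − r do not.
- All visits are attended and nobody stops the drug, so every metformin sample after baseline counts as on treatment.

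**Expected content of five of 36:** 5 × 12/36 = 1.67 on-treatment metformin samples and 5 × 24/36 = 3.33 placebo or baseline samples.

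**Formulas.** With N units in the frame, a of them from metformin responders and b from metformin nonresponders:
- P(at least one of each) = 1 − [C(N−a,5) + C(N−b,5) − C(N−a−b,5)] / C(N,5)
- P(at least one responder unit) = 1 − C(N−a,5) / C(N,5)

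**Literal reading: N = 36, on-treatment samples, a = 2r, b = 2n.** C(36,5) = 376,992.
- r = 1, both groups: 1 − (278,256 + 65,780 − 42,504)/376,992 = 0.200
- r = 3, both groups: 1 − (142,506 + 142,506 − 42,504)/376,992 = 0.357
- r = 1, any responder: 1 − 278,256/376,992 = 0.262

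| r | Both groups, on treatment | Any on-treatment responder sample |
|---|---|---|
| 1 | 20% | 26% |
| 2 | 32% | 47% |
| 3 | 36% | 62% |
| 4 | 32% | 74% |
| 5 | 20% | 83% |

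**Other frames, P(both groups), range over r = 1 to 5**
- All 36 samples, any visit counted (a = 3r, b = 3n): 34% to 59%
- 5 of the 12 participants (a = r, b = n): 40% to 69%
- 5 of the 18 metformin samples, any visit (a = 3r, b = 3n): 65% to 97%
- 5 of the 12 on-treatment metformin samples (a = 2r, b = 2n): 68% to 98%
- 5 of the 6 metformin participants (a = r, b = n): 83% to 100%

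For the aim stated in section G, at least one on-treatment responder sample, the two narrowest frames give 68% to 100% (12 on-treatment metformin samples) and 83% to 100% (6 metformin participants, one on-treatment sample each).

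**Two platforms.** If each draws independently from the 36, they share no sample with probability C(31,5)/C(36,5) = 45%.

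**The case against.** The strongest reply is that this is largely an omission. Which stored aliquots go to an exploratory assay is often settled in an analysis or laboratory plan. A random draw within metformin responders and nonresponders would satisfy both section G and section E, and a draw limited to metformin participants would mostly work. Section E also does not say that every platform must hold both groups. Serum SASP markers are measured on all subjects at all three visits, no limit of five is stated for miRNomics, and the remaining samples are stored.

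Much of this stands, and it keeps the point small. It does not remove it. The protocol does not leave selection open: it states a rule, and that rule differs from the Abstract, from section E and from the aim in its own paragraph. A later plan could add a frame, but the three descriptions would still need aligning.

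A reader might infer that the molecular map cannot be made, or that the two platforms will probably fail. The documents do not support that. The low figures belong to the literal unrestricted draw. SASP and miRNomics can supply both groups, and the stored samples allow later assays. Nor is it informative to say that the yield may lie anywhere from 0% to 100%. The 0% only restates that a frame of improved patients excludes nonresponders by definition.

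**Conclusion.** The point holds as a minor one. The selection rule for the array and the proteome disagrees with the profiled population in the Abstract and section E and with the aim in section G. Read literally, it gives the on-treatment responder and nonresponder contrast in 20% to 36% of draws, and any on-treatment responder sample in 26% to 83%.

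Those percentages rest on the assumed 6 metformin participants, 1 to 5 responders, full attendance and no discontinuation. The protocol does provide for stopping the drug, which would leave fewer on-treatment samples. The textual disagreement does not depend on any of these assumptions. Only two exploratory data sets are affected, and no frailty or safety result depends on them.

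**What to change.** Align the Abstract, section E and the Molecular markers paragraph on one profiled population. Replace both random-sample phrases with a stratified rule, for example:

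- After the last participant's final visit, the statistician draws five samples for each platform at random within response strata. The response rule is fixed before unblinding.
- Each platform's five samples come from different participants and include at least one metformin responder and one metformin nonresponder where both exist.
- The results are labelled descriptive.

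The timing matters because the investigators are blinded (section G, Blinding), and a list chosen by metformin response would reveal allocation. The different-participants condition matters because participants would otherwise repeat. Suppose one responder sample, one nonresponder sample and three of the 10 other on-treatment metformin samples are drawn. All five then come from different people in only C(4,3) × 2³ = 32 of C(10,3) = 120 selections, so a repeat occurs with probability 1 − 32/120 = 73%.

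The sponsor may instead spend some of the five slots on a placebo sample, or on baseline/12-month pairs with the different-participants condition relaxed. One pair from a responder and one from a nonresponder take four slots. Whether both platforms use the same five samples is the sponsor's choice, but it should be stated.

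Cost: wording and a selection list from the statistician, who already performs the randomization. The number of assays is unchanged. The downsides are that the samples are no longer a random cross-section of the cohort, and that these two assays wait until the end of follow-up.
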